9.4.2.3. Cardiovascular Outcomes

The following cardiovascular outcomes will be reported as both incidence proportions and exposure-adjusted incidence rates:

- Incidence of CEAC-adjudicated MACE (CV death, nonfatal myocardial infarction, and nonfatal stroke).
- Incidence of CEAC-adjudicated MACE or hospitalization for unstable angina (MACE+).

Similar methods for estimating incidence proportions and exposure-adjusted incidence rates will be applied, as described in [Section 9.4.2.2](#). In addition, the incidences of the individual MACE+ components will also be reported.

In addition, the time-to-event of MACE will be analyzed using Cox proportional hazards model with treatment as the only predictor (base model). The estimated hazard ratio and associated 95% CI will be presented. Extended models (eg, including stratification factors, other Baseline covariates, etc.) may be explored depending on the number of events observed.

Two types of analyses will be conducted: on-study analysis and on-treatment analysis. For the on-study analysis, subjects with an event during the study will contribute actual time of first occurrence, while those without an event will be censored at the end of study. For the on-treatment analysis, subjects with an event during the Treatment Period will contribute actual time of first occurrence, while those without an event during Treatment Period will be censored at the end of treatment. Sensitivity analysis may be conducted to explore different ascertainment windows for which to attribute the MACE outcome to treatment (eg, 1 month post-treatment discontinuation).

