After randomization at Baseline, subjects will be dispensed IP (lesinurad or placebo) and study-supplied XOI at the same dose as the subject's prescribed stable dose, which they will start the next day (Day 1). Subjects will take IP qd in combination with their stable dose of XOI for up to 24 months. Gout flare prophylaxis with colchicine is required from the Baseline Visit through the Month 6 study visit, while still on IP. Subjects who have a documented intolerance or allergy to colchicine or who are taking a concomitant medication contraindicated for use with colchicine (eg, P-glycoprotein [P-gp] or strong cytochrome P450 [CYP]3A4 inhibitors) are permitted to take low-dose oral corticosteroids (≤ 10 mg/day of prednisone, or prednisolone, or their equivalent) for a short course, such as through the Month 3 study visit. The use of NSAIDs for gout flare prophylaxis is not permitted. More information on gout flare prophylaxis dosing is provided in [Section 5.3](#). In order to maintain the blind, post-Baseline sUA levels will remain

blinded to the sites, subjects, and study team; additional blinding information is provided in [Section 5.5](#).

After initiating IP, subjects will return to the study site at Month 1 (± 7 days), at Month 3 (± 7 days), and every 3 months (± 7 days) thereafter until the end of the Treatment Period (Month 24 ± 7 days). Safety assessments will include an evaluation of AEs with particular focus on renal and CV events, clinical laboratory parameters (hematology, serum chemistry, urinalysis), and vital signs. Efficacy assessments will be based on an evaluation of sUA levels with assessments on tophus measurements, patient-reported outcomes, and gout flares.

[figure not shown]
Subjects who permanently discontinue IP early should complete an End of Treatment Visit as soon as possible, followed by a Post-End of Treatment Visit 1 month after the End of Treatment Visit where all AEs must be recorded. Subjects should then continue on study (and may remain on their study-supplied XO) and follow the protocol-defined schedule of events, including the End of Study Visit.

All subjects who complete the Treatment Period or who plan to withdraw early from the study should complete the End of Study Visit approximately 1 month after IP is completed or discontinued.

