5.3.2.1.2. Other Reasons, and Procedures, for Permanent Discontinuation of Investigational Product

As much as possible and permitted by the protocol, subjects should be encouraged to continue on IP for the full 24-month Treatment Period.

Subjects have the right to permanently discontinue IP at any time for any reason. Investigators may also discontinue IP if they determine that it is not in the best interest of the subject to continue. All subjects should be encouraged to remain in the study even if IP has been discontinued for any reason.

IP must be permanently discontinued if the subject meets any of the following criteria:

- Subject permanently discontinues XOI.
- Subject becomes pregnant.
- Subject initiates chronic therapy with any of the following medications:
 - valpromide, progabide, valproic acid, or other known inhibitors of epoxide hydrolase.
 - any approved ULT indicated for the treatment of gout (eg, benzbromarone, probenecid, pegloticase, commercially-available lesinurad), except those required per protocol (allopurinol and febuxostat).
 - azathioprine or mercaptopurine.
- Subject requires dialysis or kidney transplantation.
- Subject has temporarily interrupted IP for more than 3 separate episodes at any time on study due to changes in kidney function, based on any safety concern due to IP by the Investigator or Healthcare Provider, or where protocol-specified criteria for interruption have been met (ie, sCr \geq 4.0 mg/dL or an eCrCl $<$ 20 mL/min).

The date and the reason must be recorded on the appropriate Case Report Form (CRF) for all subjects who discontinue IP. If the reason is an AE, the specific AE must be identified on the CRF.

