Subjects who permanently discontinue IP early should complete an End of Treatment Visit (Section 8.3.3) as soon as possible followed by a Post-End of Treatment Visit (Section 8.4.1) 1 month after the End of Treatment Visit. Subjects should then continue on study and follow the protocol-defined schedule of events, through Month 24. The subject has the option to continue on study-supplied XOI during this time. Although all assessments are encouraged, at a minimum, it is requested that collection of AEs and collection of a blood sample for Analytes 1 (see Table 1) occur. Alternatively, if the subject does not agree to this option, a modified follow-up including, eg, regular telephone contacts or a contact at Month 24, should be arranged, if agreed to by the subject and in compliance with local data privacy laws/practices. Subjects who do not wish to continue on study after discontinuing IP should complete an End of Study Visit (Section 8.4.2) 1 month after treatment discontinuation.

If IP is permanently discontinued prior to the Month 6 study visit, then gout flare prophylaxis should also be discontinued.

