8.3. Treatment Period (Day 1 Through Month 24)

Subjects must meet all of the eligibility criteria listed in [Section 4.2](#) and [Section 4.3](#) before being randomized and starting IP, study-supplied XOI, and colchicine (as applicable). Subjects will receive IP in combination with an XOI for up to 24 months. Subjects who permanently discontinue IP early should complete an End of Treatment Visit ([Section 8.3.3](#)) as soon as possible after discontinuing IP, and a Post-End of Treatment Visit ([Section 8.4.1](#)) 1 month after the End of Treatment Visit, but should remain on the study and follow the protocol-scheduled visits.

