9.4.2.2. Renal-Related Outcomes

The following renal-related outcomes will be reported as both incidence proportions and exposure-adjusted incidence rates:

- Incidence of sCr elevation ($\geq 1.5 \times$ Baseline).
- Incidence of subjects meeting criteria (eg, based on sCr or eCrCl criteria) for treatment discontinuations.
- Incidences of renal-related and kidney stone TEAEs and SAEs.
- Prevalence of contributing factors to renal SAEs as adjudicated by the REAC.

The proportion will be calculated as the number of subjects with an outcome of interest (ie, unique subjects) during the study divided by the total number of subjects in that treatment group. The 95% CIs will be calculated based on the Wilson Score method.

The on-treatment exposure-adjusted incidence rates for an outcome of interest will be calculated as the number of subjects with that outcome of interest during the Treatment Period divided by the total duration of treatment in each treatment group (ie, “on-treatment” analysis). Similarly, the on-study exposure-adjusted incidence rates will be calculated as the number of subjects with outcome of interest during the study divided by the total duration of study in each treatment group (ie, “on-study” analysis). Exposure-adjusted incidence rates and associated exact CIs

based on the Poisson distribution will be calculated for each treatment group and reported per 100 patient-years.

Similar exposure-adjusted analysis will also be performed with the number of events as the numerator dividing by on-treatment or on-study exposure as described above.

Estimates of treatment differences with corresponding 95% CIs will be calculated. The appropriate approaches may depend on the number of events observed during blinded data review and will be detailed in the SAP prior to database lock.

Additional assessments may include the proportion of subjects who require dialysis, those who advance in their chronic kidney disease, those who have persistent decreases in eCrCl, and those who have persistent sCr elevations.

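### As worded, the on-treatment safety rates and MACE Cox model count events to Month 24 but exposure only to IP stop; the plan should define one on-treatment window and use it throughout

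*Combined protocol and SAP*

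**What the plan says.** Section 9.4.2.2 defines the on-treatment exposure-adjusted rate as the "number of subjects with that outcome of interest during the Treatment Period divided by the total duration of treatment in each treatment group". Sections 9.4.2.3 (MACE and MACE+) and 9.4.2.4 (TEAEs, SAEs and TEAEs leading to IP discontinuation) adopt the same method by cross-reference.

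For the on-treatment Cox model of MACE, Section 9.4.2.3 gives subjects with an event in the Treatment Period their actual event time, whereas "those without an event during Treatment Period will be censored at the end of treatment".

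The protocol gives the Treatment Period a fixed calendar length. Section 8.3 is headed "Treatment Period (Day 1 Through Month 24", Section 3.1 ends the period at Month 24 ± 7 days, and Section 5.3.2.1.2 says subjects should be "encouraged to continue on IP for the full 24-month Treatment Period".

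Subjects who stop IP early are asked to continue on study through Month 24, with at least AEs and the Analytes 1 panel (which includes creatinine) collected (Section 5.3.2.1.2). The TEAE definition in Section 6.11.2 has a start but no closing date. No section defines the on-treatment event window. Section 9 leaves further detail to the SAP, and the documents reviewed contain no SAP text that settles it.

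**The concern.** Two terms are used as if they were one. Events are tied to the Treatment Period, and time at risk is tied to treatment. For a subject who takes IP for 24 months they coincide. For a subject who stops early they do not.

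Take two subjects who both stop IP at Month 3 and stay in follow-up. One has a MACE at Month 20 and, read literally, enters the on-treatment Cox model as an event at Month 20. The other has no event and is censored at Month 3. After IP stop, the only stoppers left in the risk set are those who will go on to have an event, so censoring depends on the outcome. In the rate, the Month 20 event enters the numerator while neither subject's 21 off-IP months enter the denominator.

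Safety is the primary objective, and these rates carry most of the renal and all of the cardiovascular endpoints. If stopping differs by arm, the on-treatment comparison would show a difference that has nothing to do with hazard. Two programmers could also follow the text and produce different tables.

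**Working it through.** **Plan figures.** The plan states no IP discontinuation rate, MACE rate or expected event count, so there is no stated figure on this point to reproduce. What follows uses the plan's design figures and labelled assumptions.

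**Inputs from the protocol.** 300 subjects per arm (Section 9.2). A study month is 28 days (Section 8), so 24 months = 672 days and T = 672/365.25 = 1.84 years.

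**Assumptions.** A fraction d stops IP by Month 24 at a constant hazard. Every stopper is followed to Month 24. The event hazard λ is the same in both arms, on and off IP, so the true ratio is 1.00.

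**Step 1: inflation within an arm.** With stopping hazard θ, 1 − exp(−θT) = d, so θT = −ln(1 − d). Mean time on IP is d·T/[−ln(1 − d)]. The literal rate divides events to Month 24 by that shorter time, so it is inflated by T/(mean time on IP) = −ln(1 − d)/d:

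- d = 20%: 0.2231/0.20 = 1.12
- d = 30%: 0.3567/0.30 = 1.19
- d = 40%: 0.5108/0.40 = 1.28

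**Step 2: one scenario in full.** Take λ = 2 per 100 patient-years and stopping of 20% (placebo) and 35% (lesinurad).

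- Mean time on IP: 1.649 and 1.495 years.
- Probability of an event by Month 24: 1 − exp(−0.02 × 1.84) = 0.0361, or about 10.8 events per arm.
- Literal rates: 0.0361/1.649 = 2.19 and 0.0361/1.495 = 2.42 per 100 patient-years; ratio 1.10.
- Events before IP stop: about 9.7 and 8.8. So about 1.1 and 2.0 events fall after IP stop.
- Aligned rates (events and exposure both closing at IP stop): 1.96 and 1.97; ratio 1.00.

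At λ = 5 per 100 patient-years the literal rates are 5.33 and 5.88, and the ratio is again 1.10.

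**Step 3: spurious ratio, lesinurad over placebo, true ratio 1.00.** The literal rate ratio is the ratio of the two inflation factors. Cox hazard ratios come from simulation with 1,000,000 subjects per arm at λ = 2 and 5 per 100 patient-years (Monte Carlo error about ±0.01). In the last column, half of the stoppers leave the study 28 days after stopping.

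| Stopping, placebo/lesinurad | Literal rate ratio | Literal Cox HR | Cox HR, half of stoppers leave |
|---|---|---|---|
| 20%/20% | 1.00 | 0.99 to 1.01 | 0.99 to 1.01 |
| 20%/30% | 1.07 | 1.06 to 1.07 | 1.03 |
| 20%/35% | 1.10 | 1.11 to 1.12 | 1.06 to 1.07 |
| 20%/40% | 1.15 | 1.15 to 1.16 | 1.09 |
| 30%/50% | 1.17 | 1.17 to 1.18 | 1.10 |

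When events, exposure and censoring all close at IP stop, the rate ratio is 1.00 and the Cox HR 0.99 to 1.01 in every row.

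**The case against.** The strongest reply is that the intended window closes at IP stop and only the label is loose. There is good support for this.

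- The analysis is called on-treatment and its denominator is time on treatment.
- Sections 8.3.3, 8.4 and 8.4.2 contrast subjects who complete the Treatment Period with those who stop IP early, which uses the term at subject level. The Post-End of Treatment Visit sits under the Follow-Up Period.
- Section 9.4.2.3 offers a sensitivity window of one month after discontinuation, which extends the base window only if that window closes at IP stop.
- Under the literal reading, the on-treatment numerator would differ from the on-study numerator only by events after Month 24, so the two analyses would count almost the same events.

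This stands as evidence of intent. It does not cure the rule. Section 8.3.2, which is part of the Treatment Period, covers visits of subjects who have permanently stopped IP. Appendix A attaches its footnote on those subjects to the Double-Blind Treatment Period column. The sensitivity window is optional and covers MACE only, so the renal, TEAE and SAE rates have no such pointer.

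A second reply is that the effect is small beside sampling error. At about 10.8 events per arm, the 95% interval for a hazard ratio spans a factor of exp(1.96 × √(2/10.8)) = 2.3 each way. That is true for MACE at the assumed rate. But a systematic shift is not reflected in the interval, and removing it costs nothing.

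A third reply is that these are supportive, descriptive results. That also stands: Section 9.4.2 names change in eCrCl to Month 24 as the main safety estimand, and no hypothesis test on these rates is specified.

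**Conclusion.** The stated rule is faulty as worded, and its intent is unclear. Applied literally, it inflates each arm's on-treatment rate by about −ln(1 − d)/d and makes Cox censoring depend on the outcome. The between-arm distortion is about 1.07 to 1.17 over the assumed unequal-stopping scenarios and 1.00 when stopping is equal. Retention matters: at 20%/35% the Cox HR falls to about 1.06 to 1.07 if half of the stoppers leave the study. All sizes rest on a constant stopping hazard and equal event hazards on and off IP. The on-study rates, the on-study Cox model, the incidence proportions and the main eCrCl estimands are not affected.

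Three stronger conclusions might be inferred, and the documents support none of them.

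- That the protocol definitely places off-IP time in the on-treatment event window. It says such subjects remain on study, and it uses Treatment Period in both senses.
- That the lesinurad arm will look worse. Section 1.2.1 reports creatinine rises with lesinurad, and Section 9.4.2.1 foresees stopping for worsening renal function, so unequal stopping is plausible. But no discontinuation rate is given for either arm, and Section 1.2.1 adds that most rises resolved without interruption.
- That on-study laboratory rates are distorted by "a modified follow-up including, eg, regular telephone contacts or a contact at Month 24". This is a fallback for subjects who decline scheduled visits. The plan does not say how such time enters study duration, and no size can be given.

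**What to change.** In Section 9.4.2.2 and the Cox paragraph of Section 9.4.2.3, replace the reference to the Treatment Period with one defined on-treatment window: first dose of IP to last dose of IP plus a single prespecified number of days. Zero days is acceptable, with the one-month window the protocol already names kept as a sensitivity analysis. Use the same end date to count events, accumulate exposure and censor, for all subjects whether or not they have an event. State that it also governs the analyses using number of events as the numerator and the TEAE and SAE rates of Section 9.4.2.4, and repeat the definition in the SAP.

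The cost is a few sentences. No visits, data or sample size change. It should be settled before unblinding, so that the choice of window cannot be linked to the results.

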9.4.2.4. General Safety

All AEs will be coded and tabulated by Medical Dictionary for Regulatory Activities (MedDRA) System Organ Class and preferred term. Similar methods will be applied for estimating proportions and exposure-adjusted incidence rates (ie, on-study and on-treatment exposure-adjustment) of TEAE, SAEs, and TEAEs leading to permanent discontinuation of IP, as described in [Section 9.4.2.2](#).

Associated laboratory parameters such as hepatic profile, renal function, serum chemistry, hematology, and urinalysis values will be grouped and presented together. Individual subject values will be listed and values outside of the standard reference range will be flagged. Marked abnormalities meeting RCTC version 2.0 grading will also be noted. Shift tables and analyses of changes from Baseline will be included.

The change from Baseline for each of the vital signs variables will be summarized.

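### The on-study rate of TEAEs leading to permanent discontinuation of investigational product counts off-product time in which the event cannot occur, so it falls below the at-risk rate; report only the on-treatment rate for this outcome

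*Combined protocol and SAP*

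**What the plan says.** Section 9.4.2.4 (General Safety) carries the methods of Section 9.4.2.2 over to general adverse events and names the two exposure adjustments and the outcomes: "ie, on-study and on-treatment exposure-adjustment) of TEAE, SAEs, and TEAEs leading to permanent discontinuation of IP".

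Section 9.4.2.2 defines the rates. The on-treatment rate takes subjects with the outcome in the Treatment Period, "divided by the total duration of treatment in each treatment group". The on-study rate is the "number of subjects with outcome of interest during the study divided by the total duration of study in each treatment group". An event-count version uses the same denominators: "Similar exposure-adjusted analysis will also be performed with the number of events as the numerator dividing by on-treatment or on-study exposure". Treatment differences with 95% confidence intervals are to follow. No sentence ends the on-study denominator when IP stops, and neither rate is given precedence.

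Subjects who stop IP are meant to stay. Section 5.3.2.1.2 states: "Subjects should then continue on study and follow the protocol-defined schedule of events, through Month 24". Section 8.3 says that they complete the end-of-treatment visits "but should remain on the study and follow the protocol-scheduled visits". Sections 5.3.2.1.2 and 8.4 also let a stopper leave after an End of Study Visit one month later. Completers have an End of Study Visit about 28 days after Month 24 (Section 8.4.2).

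**The concern.** Permanent discontinuation of IP happens at most once per subject, and only to someone who has not already discontinued. Once a subject has stopped for any reason (own choice, loss of the xanthine oxidase inhibitor, a prohibited drug), the risk of this outcome is zero by definition. Dividing by study time averages the at-risk rate with stretches of zero.

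Safety is the primary objective, and this rate is a direct tolerability comparison that the plan wants with a between-arm difference. The better the sites keep stoppers in follow-up, as Sections 5.3.2.1.2 and 6.16 urge, the more zero-risk time enters the denominator. A reader shown two rates side by side, without guidance, could take the lower one as equally valid or as a robustness check on the other.

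**Working it through.** The plan states no rate, event count, stopping share or retention share for this outcome, so there is no figure of its own to reproduce. All such inputs below are assumptions.

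**Inputs from the protocol.** Treatment lasts 24 study months and the End of Study Visit is at Month 25 (Appendix A). A study month is 28 days (Section 8). There are 300 subjects per arm (Section 4.1).

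**Size of the dilution.** Both rates for this outcome have the same numerator, so

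on-study rate / on-IP rate = on-IP time / on-study time.

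Let stopping be exponential, with hazard a = 0.005 per study month for a TEAE (0.005 × 365.25/28 = 6.52 per 100 patient-years) and hazard o for other reasons. Mean on-IP time per subject is (1 − exp(−24(a + o)))/(a + o). If every stopper is retained, mean study time is 25 months.

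| o per month | Stop for other reasons | On-IP months | On-study rate per 100 PY | Change, all retained | Change, post-event time removed | Change, all stoppers leave after 1 month |
|---|---|---|---|---|---|---|
| 0.008 | 17% | 20.62 | 5.38 | −17.5% | −12.6% | −4.6% |
| 0.014 | 27% | 19.27 | 5.03 | −22.9% | −18.5% | −4.9% |
| 0.020 | 36% | 18.05 | 4.71 | −27.8% | −23.9% | −5.3% |

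First row: 20.62/25 = 0.825, and 6.52 × 0.825 = 5.38. The post-event column ends each subject's time at his or her own event, with other stoppers retained. What remains comes from subjects who left IP for another reason and from the last month of completers. That last month alone gives 1 − 24/25 = 4%. If 30% of stoppers leave one month after stopping, the changes (post-event time included) are −14%, −18% and −22%.

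**Effect on the comparison.** Assume 300 per arm, all stoppers retained, 30% stopping IP on lesinurad (15% for a TEAE) and 20% on placebo (8% for a TEAE). In years, treatment is 672/365.25 = 1.840 and study is 700/365.25 = 1.916.

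- On-IP time, lesinurad: 300 × 0.30 / (−ln 0.70 / 1.840) = 464.2 patient-years. Placebo: 300 × 0.20 / (−ln 0.80 / 1.840) = 494.7.
- Study time, each arm: 300 × 1.916 = 574.9 patient-years.
- On-IP rates: 45/464.2 = 9.69 and 24/494.7 = 4.85 per 100 patient-years; ratio 2.00, difference 4.84.
- On-study rates: 45/574.9 = 7.83 and 24/574.9 = 4.17; ratio 1.88, difference 3.65. The rates fall by 19.3% and 14.0%.

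With full retention the on-study ratio is 45/24 = 1.875, which is the ratio of the incidence proportions. In that case the on-study rate is the proportion divided by a constant and adjusts for no difference in exposure.

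**Direction.** Keep the 30% and 20% stopping shares, but retain 20% of lesinurad stoppers and 90% of placebo stoppers. Study time becomes 504.8 and 569.2 patient-years, the rates fall by 8.0% and 13.1%, and the ratio rises from 2.00 to 2.11. With 20% stopping and equal retention in both arms, the ratio stays at 1.00 and only the level falls (14.0% with full retention).

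**The case against.** The strongest reply is that the right rate is already in the plan. The on-treatment rate and the incidence proportion are both prescribed, the on-study rate would be labelled as such, safety is described as descriptive in Section 9.4.2, and the main safety estimands are changes in creatinine clearance. This stands: no correct estimate is missing and no test depends on the on-study rate. It does not rescue that rate. One can read it as events per year of follow-up, but with full retention it then carries nothing beyond the proportion, and with partial retention it mixes in how long zero-risk subjects happened to stay.

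Section 9 also defers further detail to the SAP. At-risk time could be settled there, but the protocol text as it stands prescribes the on-study rate for this outcome.

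Three stronger readings are tempting and unsupported.

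- A reader might infer that the arm with more stoppers always looks safer. The driver is the share of study time spent off IP, and the retention example above reverses the direction.
- A reader might infer a large spurious difference between arms with identical on-IP hazards. In the same model a ratio of 0.84 needs 9% versus 36% stopping for other reasons and every stopper retained. With 17% versus 27% it is 5.03/5.38, about 0.93. If all stoppers leave after one month, even the 9% versus 36% case gives 0.99. Nothing in the documents points to an imbalance of that size.
- A reader might extend the point to "Incidence of subjects meeting criteria (eg, based on sCr or eCrCl criteria) for treatment discontinuations" in Section 9.4.2.2. Only the rule on more than three interruption episodes needs ongoing IP use. Dialysis or transplantation (Section 5.3.2.1.2) can occur off IP. Creatinine thresholds can be observed off IP, because the Analytes 1 panel, which includes creatinine, is still requested after IP stops. Dropping the on-study rate there could hide renal deterioration that this trial exists to detect.

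**Conclusion.** The on-study exposure-adjusted rate is the wrong summary for TEAEs leading to permanent discontinuation of IP, because part of its denominator carries no risk of the event. Under the assumed exponential stopping, with about 17% to 36% leaving IP for other reasons, it is 17% to 28% too low with full retention. Off-IP time alone, after post-event time is removed, accounts for 13% to 24%. If all stoppers leave after one month, the shortfall is about 5%. These figures illustrate the size; the documents supply no stopping or retention rates.

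The between-arm ratio is distorted only when the arms differ in their share of off-IP study time, and its direction cannot be predicted from the number of stoppers alone. The on-treatment rate is planned and appropriate, so the defect is one misleading extra rate with its treatment difference. It does not extend to outcomes that can arise or be observed after IP stops.

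**What to change.** In Section 9.4.2.4 and the SAP, state that for TEAEs leading to permanent discontinuation of IP only the incidence proportion and the on-treatment exposure-adjusted rate, with its treatment difference, will be reported. Remove the on-study rate for this outcome, in both the subject-count and event-count versions.

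Keep both rates for every outcome that can occur or be observed off IP: TEAEs overall, SAEs, renal and kidney stone events, MACE, criteria based on serum creatinine or creatinine clearance, and dialysis or transplantation. If the criterion of more than three interruptions is tabulated separately, use on-treatment time for that component only.

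The cost is about one sentence in the SAP, a second if the interruption criterion is reported separately. No new data are needed, and the tables have fewer columns.
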